2.4 Secondary Endpoints

- To determine time to progression (TTP).
- To determine overall survival (OS).
- To assess pharmacokinetics and pharmacodynamics of CT-011 in combination with lenalidomide.
- To assess CT-011 immunogenicity and correlative biologic studies to assess immunomonitoring of lymphocytes subsets including T and NK cell, and *ex-vivo* assessment of immune functional activities.

2.5 Safety Parameters

Infusion related and treatment emergent toxicities per NCI CTCAE v.4

3 ELIGIBILITY CRITERIA

3.1 Inclusion Criteria

- Patients must be at least 18 years of age with evidence of relapse or refractory disease as defined by IMWG criteria and measurable disease as defined by any of the following:
 - Serum M-protein \geq 0.5 g/dl (\geq 10 g/l)

- Urine monoclonal protein \geq 200 mg/24h
 - Involved FLC level \geq 10mg/dl (\geq 100mg/l) and an abnormal serum free light chain ratio (<0.26 , or >1.65)
 - Measurable biopsy proven plasmacytoma (should be measured within 28 days of registration to study)
- Patients must have had at least 2 prior line of therapy.
- Patients must not have had progression of disease on lenalidomide 25 mg. Stable disease on lenalidomide is permitted.
- Patient may be enrolled at any time from last line of therapy.
- Patients must have ANC $>$ 1000/ μ L; Platelets \geq 75,000/ μ L, If plasma cell percentage on bone marrow biopsy aspirate or core is $>$ 30%, platelet eligibility requirement will be adjusted to 60,000/ μ l.
- Patients must have adequate hepatic function as evidenced by: total bilirubin \leq 1.5 mg/dL, alkaline phosphatase \leq 3X the ULN, AST/ALT \leq 2X the ULN
- Patients must have adequate renal function as evidenced by serum creatinine \leq 2mg/dL or calculated creatinine clearance of \geq 40ml/min within 14 days of registration using MDRD formula.
- Patient must be able to swallow capsule or tablet.
- Patients must provide informed consent.
- Patients must have a left ventricular ejection fraction $>$ 30%, no uncontrolled arrhythmias or New York Heart Association class III-IV heart failure.
- Patients must have a Karnofsky performance status \geq 70.
- A negative pregnancy test will be required for all women of child bearing potential. Breast feeding is not permitted.
- Fertility requirements
 - Female patients with child bearing potential must have a negative pregnancy test within 7 days before starting treatment drugs.
 - Male patients must agree to use an adequate method of contraception for the duration of the study and for 90 days after study therapy discontinuation.
 - Female patients must be either post-menopausal, free from menses \geq 2 yrs, surgically sterilized, willing to use two adequate barrier methods of contraception to prevent pregnancy, or agree to abstain from sexual activity starting from screening and continuing through 90 days after study therapy discontinuation.
 - Female patients of child bearing potential must agree to comply with the fertility and pregnancy test requirements dictated by the Rev-Assist program.\

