5.8.6 Schedule of Events^a

Investigations	Screening	C1D3	C1D4	C1D6	C1D10	C1D17	C2D3	C3D3	C5D3	CxD3	End of Tx ^b	Follow Up ^p
History, physical examination, concomitant medication review	X	X					X	X		X	X	
Informed written consent	X											
Confirmation of disease relapse and prior treatment	X											
Skeletal survey (CT or MRI as clinically indicated) ^c	X										X	
MUGA or ECHO	X											
β-hCG ^d	X	X										
Toxicity evaluation	X	X					X	X		X	X	X
CBC / differential / platelets ^e	X	X					X	X	X	X ^f	X	
PTT, INR, TSH ^e	X											
BMP, glucose, magnesium ^e	X	X					X	X		X		
LFTs	X	X					X	X		X		
Beta 2 microglobulin ^g	X							X			X	
12-lead ECG ^h	X							X				
Serum monoclonal protein assessments ⁱ	X	X ⁱ					X ⁱ	X ⁱ		X ⁱ	X ⁱ	
24hr urine for creatinine clearance	X											
24hr urine monoclonal protein and immunofixation ^j	X	X ^j					X ^j	X ^j		X ^j	X ^j	
BM biopsy, unilateral ^k	X								X ^k		X ^k	
CT-011 Given		X					X	X	X	X		
Prescribe lenalidomide via RevAssist ^l	X											
T-cell, NK-cell, and CD14 Correlative studies ^m	X	X	X	X	X	X	X	X	X	X	X	X

CT-011 PK ⁿ		X	X	X	X	X	X				
ADA (immunogenicity) ^o	X										

- a. With the exception of PK samples, all other time points have a +/- 4 day window to accommodate weekends, holidays, and for patient convenience.
- b. Off study correlates will be done. In addition, continued T-cell correlate will be done at 1,3, and 6 months after removal from study
- c. Skeletal survey will be done at baseline and may be done at evidence of progression of disease. CT scan will be done to document size of plasmacytoma if this is the only measurable disease.
- d. Female patients of childbearing potential (FCBP, defined in section 8.5) must have a negative pregnancy test (β -hCG) as required by the RevAssist program. Lenalidomide and dexamethasone will start on day 1 of each cycle. Patients do not need to be in clinic to initiate this as all patients would have been exposed to both. Lenalidomide will be ordered for the next cycle. A pregnancy test (urine or serum β -HCG) will also be ordered at this time. Patients must have a negative β -HCG result prior to starting lenalidomide on day 1 of each cycle.

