The proportion of responses (partial and complete) will be calculated out of all eligible patients who receive any treatment in that disease group who are included in the phase II assessment. Assuming the number of responses is binomially distributed, 95% binomial confidence intervals will also be calculated for the estimate of the proportion of responses. All adverse events will be summarized by the NCI CTCAE v. 4 criteria, and tabulated across all patients who received any treatment with a focus on severe (grade 3+) adverse events and toxicities (i.e. those deemed at least possibly related to study treatment). In addition, we will summarize the proportion of patients who received dexamethasone after being stable disease but without response after 2 cycles of therapy. We will descriptively summarize how many of these patients were converted to response after the addition of dexamethasone. Since the addition of dexamethasone is part of the overall treatment regimen that is dependent on treatment outcome at a certain time point, we will not make other adjustments to the study design to evaluate these patients separately outside of this descriptive summarization of whether or not they received the dexamethasone. We will evaluate other clinical outcomes such as progression-free survival and overall survival using the methods of Kaplan-Meier, although these analyses will be exploratory and primarily to help describe the cohort itself.

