6.5 Prohibited treatments

The use of concomitant chemotherapy, biological therapy (including cytokines, however erythropoietin is allowed), and steroid therapy (inhaled, oral or topical steroids for treating mild to moderate asthma, allergies or ocular inflammations, typically at ≤ 500 ug/day of fluticasone or equivalent are allowed), is prohibited as long as the patient is on the study and must have been stopped at least 4 weeks prior to first dose administration. Concomitant radiotherapy during treatment for palliation of pain may be permissible with prior approval of study PI. Radiotherapy should be directed to a localized area (involved field radiotherapy) and cannot exceed 25Gy. Radiotherapy to more than one localized area at a time is not allowed. Participation in any clinical study involving any medications or treatments, whether approved or investigational, is prohibited.

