Appendix B: IMWG Response Criteria

Serum and urine M-protein estimates will be performed every 4 weeks; except for assessment of CR, patients with measurable disease restricted to the SPEP (or UPEP) will need to be followed only by SPEP (or UPEP). Responses will be assessed according to the criteria of the International Myeloma Working Group⁶¹, and characterized as follows:

Response Category	Response Criteria ^a
SCR	CR as defined below plus 
 • Normal FLC ration and • Absence of clonal cells in bone marrow^b by immunohistochemistry or immunofluorescence^c
CR	Negative immunofixation on the serum and urine and disappearance of any soft tissue plasmacytomas and $\leq 5\%$ plasma cells in bone marrow ^b
VGPR	Serum and urine M-protein detectable by immunofixation but not on electrophoresis or 90% or greater reduction in serum M-protein plus urine M-protein level < 100 mg per 24 hours
PR	$\geq 50\%$ reduction of serum M-Protein and reduction in 24 hour urinary M-protein by $\geq 90\%$ or to < 200 mg per 24 hours If the serum and urine M-protein are unmeasurable ^d a $\geq 50\%$ decrease in the difference between involved and uninvolved FLC levels is required in place of the M-protein criteria If serum and urine M-protein are unmeasurable, and the serum free light assay is also unmeasurable, $\geq 50\%$ reduction in plasma cells is required in place of M-protein provided baseline bone marrow plasma cell percentage was $\geq 30\%$ In addition to the above, if present at baseline a $\geq 50\%$ reduction in the size of soft tissue plasmacytomas is also required
SD^e	Not meeting criteria for CR, VGPR, PR, or progressive disease
Relapse Category^f	Relapse Criteria
Progressive disease	Requires only one of the following: Increase of $\geq 25\%$ from baseline in: 
 • Serum M-component and/or (the absolute increase must be ≥ 0.5 g/dl)^g • Urine M-component and/or (the absolute increase must be ≥ 200 mg/24 hours) • In patients without measurable serum and urine M-protein levels the difference between involved and

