	
uninvolved FLC levels, the absolute increase must be $> 10 \text{ mg/dl}$.
 
 • Bone marrow plasma cell percentage, the absolute % must be $\ge 10\%$^h. • Definite development of new bone lesions or soft tissue plasmacytomas increase in the size of existing bone lesions or soft tissue plasmacytomas. • Development of hypercalcemia (corrected serum calcium $> 11.5 \text{ mg/dl}$ or 2.65 mmol/l) that can be attributed solely to the plasma cell proliferative disorder.
Clinical relapse (Not used for TTP or PFS)	Clinical relapse requires one or more of: 
 • Development of new soft tissue plasmacytoma or bone lesions • Definite increase in the size of existing plasmacytomas or bone lesions. A definite increase is defined as a 50% (and at least 1 cm) increase as measured serially by the sum of the products of the cross-diameters of the measurable lesion • Hypercalcemia ($> 11.5 \text{ mg/dl}$ [2.65 mmol/l]) • Decrease in hemoglobin of $\ge 2 \text{ g/dl}$ (1.25 mmol/l) • Rise in serum creatinine by 2 mg/dl or more ($177 \mu\text{mol/l}$ or more)
Relapse from CR ⁱ	Any one or more of the following: 
 • Reappearance of serum or urine M-protein by immunofixation or electrophoresis • Development of $\ge 5\%$ plasma cells in the bone marrow^j • Appearance of any other sign or progression

a. All response categories require two consecutive assessments made at anytime before the institution of any new therapy; all categories also require no known evidence of progressive or new bone lesions if radiographic studies were performed. Radiographic studies are not required to satisfy these response criteria.

b. Confirmation with repeat biopsy not necessary.

c. Presence/absence of clonal cells is based upon the κ/λ ratio by immunohistochemistry and/or immunofluorescence requires a minimum of 100 plasma cells for analysis. An abnormal ration reflecting presence of an abnormal clone is κ/λ of $> 4:1$ or $< 1:2$.

d. Applicable only to patients who have 'measurable' disease defined by at least one of the following three measurements: Serum M-protein $\ge 1 \text{ g/dl}$, Urine M-protein $\ge 200 \text{ mg/24hour}$, Serum FLC assay involved FLC level $\ge 10 \text{ mg/dl}$ provided serum FLC ration is abnormal.

e. Not recommended for use as an indicator of response; stability of disease is best described by providing the time to progression estimates).

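### A patient who enters on a plasmacytoma alone, with baseline marrow plasma cells below 30%, has no size-based partial response in Appendix B, and the CT required for such patients has no cycle-4 time point

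*Combined protocol and SAP*

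**What the plan says.** **Entry.** Section 3.1 (and the synopsis) asks for "measurable disease as defined by any of the following" and lists four items. The first three are serum M-protein, urine M-protein and involved free light chain (FLC). The fourth stands on its own: "Measurable biopsy proven plasmacytoma (should be measured within 28 days of registration to study".

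**Response.** Appendix B, footnote d, recognises only "disease defined by at least one of the following three measurements": serum M-protein, urine M-protein and FLC. The PR row works down a ladder. M-protein comes first, and FLC replaces it if M-protein is unmeasurable. If FLC is unmeasurable too, a halving of marrow plasma cells applies: "reduction in plasma cells is required in place of M-protein provided baseline bone marrow plasma cell percentage was" at least 30%. Only after these steps does the row add that, where a plasmacytoma was present at baseline, a 50% "reduction in the size of soft tissue plasmacytomas is also required". CR needs negative immunofixation, disappearance of plasmacytomas and no more than 5% marrow plasma cells.

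**Imaging.** The Schedule of Events (section 5.8.6) marks the skeletal survey/CT/MRI row at screening and end of treatment only. Footnote c adds: "CT scan will be done to document size of plasmacytoma if this is the only measurable disease". It names no on-treatment visit. Footnote k schedules a marrow at the end of cycle 4 for non-secretory disease.

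**Analysis.** The decision rule in section 6.1.2 counts responses after 4 cycles among 29 evaluable patients: Promising at 12 or more, Not promising at 9 or fewer. The same section says that the proportion of partial and complete responses "will be calculated out of all eligible patients who receive any treatment". Section 6.3 defines a response rate that also counts stable disease, over per-protocol patients.

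**The concern.** The entry criteria admit a kind of measurable disease that the response criteria do not use as a measure of response. For a patient on this route with marrow below 30%, a large but incomplete shrinkage of the only measurable lesion is stable disease, and so a non-response under section 6.1.2. The criteria are also lopsided: growth of an existing plasmacytoma is listed in Appendix B as sufficient for progression, so the same lesion can fail the patient but cannot earn a PR.

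The route that clearly remains, CR, depends on showing that the lesion has gone. Nothing fixes a scan at the cycle-4 assessment on which the primary decision rests.

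At stake is the primary endpoint. Each such patient adds to the denominator with little chance of adding to the numerator, for reasons unrelated to drug activity. That makes Promising harder to reach.

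**Working it through.** **Step 1: does a plasmacytoma-only patient reach the end of the PR ladder?** Such a patient has failed the other three entry thresholds:

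| Marker | Entry threshold, section 3.1 | Measurable, Appendix B footnote d |
|---|---|---|
| Serum M-protein | 0.5 g/dl | 1 g/dl |
| Urine M-protein | 200 mg/24 h | 200 mg/24 h |
| Involved FLC, abnormal ratio | 10 mg/dl | 10 mg/dl |

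A value below each entry threshold is also below the footnote d threshold, so all three markers are unmeasurable. Only the marrow step is left, and it is open only if baseline marrow plasma cells were at least 30%. Below 30%, the row gives no base criterion to which the plasmacytoma condition could be added.

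**Step 2: reproduce the design.** Inputs from section 6.1.2: n = 29, null rate 0.25, alternative 0.50, cut-offs 12 and 9. With X ~ Binomial(29, p):

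- type I error = P(X ≥ 12 | 0.25) = 0.039 (stated 4%)
- type II error = P(X ≤ 9 | 0.50) = 0.031 (stated 3%)
- eta = P(X ≤ 9 | 0.25) = 0.834 (stated 0.83)
- pi = P(X ≥ 12 | 0.50) = 0.868 (stated 0.87)

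All four agree with the plan.

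**Step 3: effect of k patients who cannot score.** Assumptions: k of the 29 never respond, and the others respond at p. Then X ~ Binomial(29 − k, p), with cut-offs unchanged. The apparent response rate at p = 0.50 is 0.50 × (29 − k)/29. The documents do not give k.

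| k | Apparent rate when p = 0.50 | P(Promising), p = 0.50 | P(Not promising), p = 0.50 | Type I error, p = 0.25 |
|---|---|---|---|---|
| 0 | 0.500 | 0.868 | 0.031 | 0.039 |
| 1 | 0.483 | 0.828 | 0.044 | 0.029 |
| 2 | 0.466 | 0.779 | 0.061 | 0.022 |
| 3 | 0.448 | 0.721 | 0.084 | 0.015 |

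The first three such patients cost 0.040, 0.049 and 0.058 of pi in turn. For a given k this is an upper bound on the loss, because it gives these patients no chance of CR.

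**The case against.** The strongest reply is that these patients are not shut out. That is largely right, and it limits the point:

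- A reader might infer that no PR is open to any of them, or that most are automatic non-responders. The documents do not support either. With baseline marrow of at least 30%, PR by marrow is available (with the plasmacytoma condition added). CR is open to all of them. Footnote k supplies a cycle-4 marrow if the disease is non-secretory. Neither the number of such patients nor their marrow percentages is given.
- A reader might infer that very good partial response (VGPR) is closed too. As written, the VGPR row carries no plasmacytoma condition, so a patient with M-protein seen only on immunofixation could meet it literally.
- A reader might infer that the lesion will not be measured at cycle 4. Footnote c requires a CT for exactly this group, and response must be assessed after cycle 4. The gap is that the CT has no stated time. Appendix B footnote a also says imaging is not needed to satisfy the criteria, so nothing obliges a site to scan then.
- Section 6.5 says "Concomitant radiotherapy during treatment for palliation of pain may be permissible with prior approval of study PI". One might infer that irradiating the sole lesion distorts the result. That is speculative, since use is limited to localised pain palliation, and a false CR would raise the rate, not lower it. It is no part of this point.
- The bias depends on the definition used. Under section 6.3, stable disease would make many of these patients responders. If they were declared not evaluable and accrual continued to 29 evaluable patients, the loss would vanish. If they were dropped without replacement, the cut-off of 12 would apply to fewer patients, and pi would fall as in the table (0.828 at 28).

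The last item does not rescue the plan. It shows that the same patient is a non-responder under section 6.1.2 and may be a responder under section 6.3, although Appendix B footnote e advises against using stable disease as an indicator of response. Evaluable is not defined for this group.

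**Conclusion.** The point holds in a limited form. The entry list and the PR row do not match for patients whose only measurable disease is a plasmacytoma and whose baseline marrow plasma cells are below 30%. For them, essentially only CR can count under section 6.1.2, and the required CT has no time point at the primary assessment. If they stay in the 29-patient denominator, the response rate is biased downwards.

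The size is unknown because the number of such patients is not given and may be zero. On the assumptions in step 3, one to three of them would lower the probability of Promising from 0.868 to between 0.828 and 0.721. Type I error would fall from 0.039 to between 0.029 and 0.015. The error is therefore conservative: it can hide an active regimen but does not make a false Promising more likely. It merits correction because a written rule misclassifies response on the primary endpoint and the remedy is small.

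**What to change.** **Preferred.** Add one sentence to the PR row of Appendix B: for patients whose only measurable disease is a plasmacytoma, a reduction of at least 50% in its size is PR. In footnote c and the grid of section 5.8.6, place the CT already required for these patients at the end-of-cycle-4 response assessment. Since Appendix B footnote a asks for two consecutive assessments for every response category, say whether a size-based PR needs a second scan. Cost: wording, and a fixed time for a CT that the plan already calls for (plus a second scan if confirmation is wanted).

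**Alternative.** Make the list in section 3.1 match Appendix B, so that a plasmacytoma qualifies only alongside one of the three measurable markers. Cost: wording, and the loss of patients who could enter by this route only.

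**Either way.** Reconcile sections 6.1.2 and 6.3. State one denominator for the primary response rate (evaluable, eligible and treated, or per protocol), define evaluable, and say whether stable disease counts as response. This costs wording only.

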4.4 Duration of Treatment

Patient can continue study treatment at the treating physician's discretion. Patients achieving at least a stable disease can continue treatment until one of the following is reached:

- Progression of disease
- Death
- Unacceptable toxicity
- Patient decision
- Treatment delay greater than 4 weeks.

Overall response will be assessed after 4, 8, and 12 cycles. If disease progression is observed at the end of Cycle 4 evaluation, all study therapy will be discontinued. In addition, study therapy will be discontinued at the time of disease progression as noted above. Otherwise patient can continue treatment until one of the above endpoints is reached.

Following the 30-day post-treatment follow-up assessment, additional evaluations will occur once per month (unless subject discontinued due to progression) until the earliest of the following events:

- Disease progression,
- The time of initiation of new therapy,
- Death or study completion.

Study completion is defined as 30 days after the last subject remaining on study medication discontinues study medication.

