5.2 Lenalidomide (RevlimidTM)

5.2.1 Lenalidomide Administration and Schedule

Lenalidomide will be given orally. Schedule as shown in table 5.1

The first dose level starts at 15 mg days 1-21 of a 28 day cycle.

If a dose is missed or vomited up, the dose will not be made up.

Beginning by day 1 of cycle #2 and on day 1 of every cycle thereafter, while all six conditions below have been met, patients will be evaluated for lenalidomide dose escalation.

For patients that:

- Never had a lenalidomide dose reduction due to a toxicity that was probable or definitely related to lenalidomide.
- Maintained platelet count $\geq 50,000$ at all times in the previous cycle
- Minimum ANC $\geq 1,000$ at all times in the previous cycle
- No clinically significant grade 2 or greater non-hematologic toxicities in the previous cycle
- Not yet reached the maximum daily dose of 25 mg of lenalidomide
- Are willing to undergo dose escalation of lenalidomide.
- Serum Creatinine maintained at ≤ 2 mg/dL as in initial eligibility

Then the patient's dose for lenalidomide will be increased by 5 mg per cycle for days 1-21 of a 28 day cycle. If any of the criteria are not met, then no lenalidomide dose escalations will occur during this cycle.

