5.2.2 Lenalidomide dose levels

Before each drug dose, the patient will be evaluated for possible toxicities that may have occurred after the previous dose(s). Toxicities are to be assessed according to the NCI Common Terminology Criteria for Adverse Events (CTCAE), Version 4.0. Dose modifications or delays will be done based on the toxicity experienced during a cycle of therapy or newly encountered on day one of a cycle.

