5.3.1 Table 5.1 Adverse events and Dose Adjustment of drugs

Neutropenia	Grade 3 or greater on day 1 of cycle: delay and monitor CBC weekly; if resolves to \leq grade 2 within 4 weeks, resume lenalidomide with 5mg dose reduction. If grade 3 or greater during a cycle, hold lenalidomide for the remainder of the cycle. Resume with 5mg dose reduction for subsequent cycles. G-CSF or GM-CSF are not to be used to avoid dose reductions but can be used for treatment of febrile neutropenia
Febrile Neutropenia	Hold lenalidomide for the remainder of the cycle. Consider G-CSF administration until there is adequate count recovery $ANC \geq 1000/\mu L$ + absence of fever. If neutropenia resolves \leq grade 2, resume lenalidomide at 5 mg dose reduction for subsequent cycles.
Thrombocytopenia	If grade 3 or greater, hold lenalidomide for the remainder of the cycle and until platelets $\geq 50,000/\mu L$. Then resume lenalidomide at 5 mg dose reduction for subsequent cycles.
Anemia	For grade 3 or greater, hold lenalidomide for the remainder of the cycle and until hemoglobin recovers to \leq grade 2.
Fatigue (asthenia, malaise) Lenalidomide or dexamethasone	For intolerable grade 2 or grade 3-4, hold the protocol therapy thought to be probable or definitely related to the reaction until resolves to \leq grade 1, then resume protocol therapy with dose reduction of implicated protocol therapy by one dose level (5 mg for lenalidomide and/or 50% for dexamethasone).
Rash Lenalidomide	If grade 3 or greater, hold lenalidomide until resolves to \leq grade 2, then resume protocol therapy. In the instance of intolerable recurrent rash, stop implicated drug but may continue on study.
Renal insufficiency	For patients with calculated or measured GFR $<30\text{ml/min}$, lenalidomide should be held until creatinine returns to baseline
Venous Thromboembolism	All protocol should be held until the patient is adequately anti-coagulated. Patients with recurrent thrombosis despite adequate anti-coagulation should be removed from protocol therapy.
Suspected Pregnancy	Protocol therapy should be held until pregnancy is ruled out. Discontinue all protocol therapy if pregnancy is positive
Dyspepsia, gastric or duodenal ulcer, gastritis Grade 1-2 (requiring medical management)	Treat with H2 blockers, sucralfate, or omeprazole. If symptoms persist despite above measures, decrease dexamethasone dose by 1 dose level

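### Entry and escalation set a creatinine limit but no GFR floor, so a patient can start below the GFR of 30 at which Table 5.1 holds lenalidomide, and that hold releases with no renal recovery or is not triggered

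*Combined protocol and SAP*

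**What the plan says.** **Entry (Section 3.1; synopsis, Eligibility).** "Patients must have adequate renal function as evidenced by serum creatinine" no higher than 2 mg/dL, or a calculated clearance of at least 40 ml/min by MDRD within 14 days of registration. The two limbs are alternatives. Section 3.2 excludes no level of GFR, and the cycle-start list in Section 5.6 names no level of renal function.

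**Escalation (Section 5.2.1).** From cycle 2, a patient below 25 mg who meets every listed condition goes up by 5 mg per cycle. The one renal item is creatinine maintained at or below 2 "mg/dL as in initial eligibility". Every item binds: "If any of the criteria are not met, then no lenalidomide dose escalations will occur during this cycle".

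**Hold (Table 5.1, renal insufficiency row).** "For patients with calculated or measured GFR" below 30 ml/min, "lenalidomide should be held until creatinine returns to baseline". No formula is named for the calculated value.

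**Scope of dose changes (Section 5.2.2; Section 5.3.2 is similar).** Modifications are made "based on the toxicity experienced during a cycle of therapy or newly encountered on day one of a cycle".

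**Screening (Section 5.8.6).** A 24-hour urine creatinine clearance is collected, but no eligibility rule uses it.

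**The concern.** The plan treats a GFR below 30 as a reason to stop lenalidomide, yet it can enrol a patient who is already there. Section 9.2 says that about two-thirds of the drug leaves unchanged in the urine, so renal function bears directly on exposure. For such a patient the entry, escalation and hold rules point in different directions, and sites could reasonably act differently. What is at stake is the dosing and safety of a few patients and consistent conduct across sites.

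**Working it through.** The plan states no computed figure on this point. The check has two parts: whether the rules conflict as written, and whether the conflict can occur in a real patient.

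**1. The rules applied to four patients**

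| Patient | Entry (3.1) | Table 5.1 row |
|---|---|---|
| Enters at GFR 30 or above, falls below 30 on study | Eligible | Works: held until creatinine is back at a baseline that corresponds to GFR of at least 30 |
| Enters below 30, creatinine stable, row read by patient status | Eligible if creatinine is at most 2 | Held, but creatinine is already at baseline, so release is met with no renal change |
| Same patient, row read as covering on-study toxicity only (5.2.2, 5.3.2, table title) | Eligible | Not triggered by the entry GFR |
| Enters below 30, then worsens on study | Eligible | Held, then released at a baseline still below 30 |

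The conflict lies in the last three rows. It needs no numerical assumption beyond the existence of a patient with creatinine at most 2 and GFR below 30.

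**2. Can such a patient exist?**

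The plan names MDRD but does not print it. Assumed here: the four-variable form, read as ml/min as the plan does,

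GFR = k × Scr^(−1.154) × age^(−0.203) × 0.742 if female × 1.212 if the race term applies, with k = 175 or 186.

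Worked example, woman aged 65, creatinine 2.0, no race term, k = 175: 175 × 0.449 × 0.429 × 0.742 = 25.0.

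Results at creatinine 2.0 mg/dL (the entry limit), ages 45 to 75:

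| Group | k = 175 | k = 186 |
|---|---|---|
| Women, no race term | 26.9 to 24.3 | 28.6 to 25.8 |
| Women, race term | 32.7 to 29.4 | 34.7 to 31.3 |
| Men, no race term | 36.3 to 32.7 | 38.6 to 34.8 |

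Solving GFR = 30 for women without the race term gives creatinine 1.82 to 1.67 (k = 175) or 1.92 to 1.76 (k = 186), inside the entry limit. Men without the race term stay above 30 at creatinine 2.0.

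**3. Sensitivity to the formula**

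The hold names no formula, so a site could use another. With Cockcroft-Gault, (140 − age) × weight / (72 × Scr) × 0.85 if female, at creatinine 2.0 and an assumed 60 kg, men run from 39.6 at age 45 to 27.1 at 75 and are below 30 from about age 68. Women run from 33.6 to 23.0 and are below 30 from about age 55. At 80 kg neither sex falls below 30 by age 75 (men 36.1, women 30.7).

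The formula can change the decision. A 75-year-old man of 60 kg with creatinine 1.9 and no race term has MDRD 34.7 (k = 175) or 36.9 (k = 186), but Cockcroft-Gault (65 × 60)/(72 × 1.9) = 28.5.

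**4. Reach of the escalation gap**

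Main-cohort starting doses are 15, 15, 25 and 25 mg (Table 5-1 in Section 5.1.1). The escalation condition is moot at 25 mg, so it has no effect for patients starting in cohorts 3 and 4, or in phase II if 25 mg is selected. From 15 mg, two steps of 5 mg reach the cap.

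**5. Reach into the design**

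DLTs count in cycle 1 only and escalation starts at cycle 2, so escalation cannot alter a cohort's DLT count. The phase II rule depends only on 29 patients, its response cut-offs and the rates 25% and 50%. Recomputed, it gives alpha 0.039, beta 0.031, eta 0.834 and pi 0.868, against the plan's 4%, 3%, 0.83 and 0.87. Renal function enters none of these.

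**The case against.** The strongest reply is that the Table 5.1 row is written by patient status, unlike neighbouring rows keyed to toxicity grade. Read that way it does hold a patient who enters below 30, and the defect is only a badly drafted release clause. There are safeguards too. The 24-hour clearance is a screening item, and Section 7.5 requires subsites to submit the screening items before registration, so a low value should be seen. Creatinine is checked every two weeks for two months and then monthly. The investigator may decline or withdraw a patient (Sections 3.2, 5.7, 10.7), and Appendix E provides continuous safety review. Clinically significant grade 2 or higher non-hematologic toxicity in the previous cycle also blocks escalation, which could catch new renal toxicity.

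Much of this stands, and it makes unnoticed entry less likely. But none of these safeguards states a GFR level, and monitoring for change does not settle a low GFR present at the start. Even on the status reading, release is met at once.

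Several stronger readings are tempting and are not supported:

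- A reader might infer that the hold can never act on a patient who enters below 30. It can, if that patient worsens.
- A reader might infer that a site that keeps holding must drop the patient after four weeks. The item "Treatment delay greater than 4 weeks" in Section 4.4 sits in a list for patients with at least stable disease, and the four-week rule in Section 5.6 concerns treatment-related toxicity. Neither clearly covers a hold on cycle 1 day 1 for a pre-existing low GFR.
- A reader might infer that the plan directs overdosing. It does not; it leaves rules that conflict.
- Section 5.2.1 says "while all six conditions below have been met, patients will be evaluated for lenalidomide dose escalation" and then lists seven items. That is a clerical slip with no bearing on this point.

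**Conclusion.** The conflict between the rules is real and should be fixed. It rests on the text of Section 3.1, Section 5.2.1 and Table 5.1, not on any formula. Its size does rest on assumptions: with the MDRD coefficients above, it concerns mainly women with creatinine of about 1.7 to 2.0 mg/dL. Smaller, older men enter only under Cockcroft-Gault, which the plan does not name, and at an assumed low weight. The documents give no distribution of renal function, so the number affected is unknown; it is probably small.

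A reader might go on to infer that the MTD or the phase II result is compromised. The documents do not support that: the MTD rule, the error rates and the sample size do not change, and nothing in the plan links baseline GFR to DLT or response rates. This is a patient-safety and consistency problem in the dosing rules.

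**What to change.** Use one definition of GFR throughout: calculated means MDRD, the formula the plan already names, and measured means an adequate 24-hour collection where one is available. Then:

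1. **Section 3.1 and synopsis.** Keep both limbs and add: *and no calculated (MDRD) or available measured GFR below 30 ml/min*.
2. **Section 5.2.1.** Add *GFR at least 30 ml/min (MDRD)* to the escalation conditions. The count of conditions can be corrected in the same edit.
3. **Table 5.1.** Name MDRD for calculated GFR, and release the hold only when *creatinine returns to baseline and GFR is at least 30 ml/min*.

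Naming the formula matters. Without it, the 75-year-old man above could pass an MDRD entry check and be held by a site using Cockcroft-Gault, now with a stricter release.

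**Cost.** An amendment to three sections and the synopsis. No new scheduled test is needed, since creatinine and the screening 24-hour collection are already in Section 5.8.6; an inadequate collection may need repeating. A small group with creatinine at most 2 but GFR below 30 becomes ineligible. Any patient already enrolled below 30 would stay held unless GFR rises, so the amendment should say how to manage them.

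The floor of 30 is the plan's own hold threshold. Making MDRD 40 mandatory would cost more: over ages 45 to 75, without the race term, it would exclude women above creatinine of about 1.30 to 1.50 and men above about 1.68 to 1.94. A floor above 30 is a separate clinical decision.
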